1.1 Study Schematic

1.2 Schedule of Assessments

Assessment Period	Screening Up to 21 days		Treatment* 52 weeks							Follow-Up 14 days		Unscheduled Visit
	1	2 ¹	3	4, 5, 6, 7, 8, 9 (Flexible)	10, 13, 17, & 20	11 & 12	14-16 & 18-19	21/ET ²	22/EOT	23	24/EOS	
Dayse	≤ 21 days prior to Visit 3		1	Every 4-10 Days after previous visit	Every 30 (- 3)	Every 30 (- 3)	Every 30 (- 3)	D357 (+ 3)	D364 (+ 3)	72 hours	14 (± 2)	
Written informed consent	X											
Inclusion/exclusion criteria	X	X	X									
Demographics ³	X											
PHQ-8 ⁴	X											
Medical history ⁵	X											
Alcohol breath test ⁶	X											
Physical examination ⁷	X											
Vital signs ⁸	X		X	X	X				X	X		X
12-lead electrocardiogram ⁹	X				X				X			X
Clinical laboratory tests ¹⁰	X		X	X	X	X		X	X	X	X	X
Pregnancy test ¹¹	X		X		X				X			X
Urine drug screen ¹²	X		X	X	X							
eC-SSRS ¹³	X		X		X			X	X			
Taper opioid analgesics ¹⁴		X										
Dose titration assessment				X								
mBPI-SF ¹⁵			X	X	X	X	X		X			X
COWS		X ¹⁶	X ¹⁶					X	X	X	X	X
SOWS ¹⁷		X						X	X	X	X	
PK blood sample collection			X ¹⁸	X ¹⁹	X	X		X	X			X
Discontinue current analgesics			X									
Dispense/review/collect/instruct study drug			X	X	X	X	X	X ²⁰	X ²¹			X
Opioid side effect training			X									
Abuse & diversion assessment				X	X	X	X		X			X
Concomitant medications ²²			←									X
Adverse events ²²			←									X

Abbreviations: ALP, alkaline phosphatase; ALT, alanine aminotransferase; AST, aspartate aminotransferase; BMI, body mass index, COWS, Clinical Opiate Withdrawal Scale; eC-SSRS, electronic Columbia–Suicide Severity Rating Scale; ECG, electrocardiogram, EOS, end of study; EOT, end of treatment; ET, early termination; mBPI-SF, modified Brief Pain Index-Short Form; MSE, morphine sulfate equivalent; NRS numerical rating scale; PHQ-8, Personal Health Questionnaire Depression Scale PK, pharmacokinetic; SOWS, Subjective Opiate Withdrawal Scale; TBL, total bilirubin.

* If at any time a subject does not tolerate study drug between protocol-mandated visits in the Treatment Period, per Investigator discretion, an unscheduled visit should occur.

FOOTNOTES:

1. There is no Visit 2 for Rollover Subjects.
2. If a subject was dosed with study drug and discontinues from the study before completing all of the scheduled assessments, then assessments for Visit 21/ET and all safety follow-up procedures should be completed for this subject.

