6.2 Treatment Period (Visits 3-20)

At Visit 3, subjects will be evaluated for entry into the Treatment Period. The Investigator or qualified sub-Investigator will complete the COWS ([Wesson, 2003](#)). The subject must score ≤ 12 to continue in the Treatment Period. Subjects who score greater than 12 will complete their Screening Period and end study participation and will be treated appropriately for withdrawal according to the investigators clinical practice. A Rollover Subject's last COWS assessment during Study 14-181-07 or Study 14-181-12 will satisfy this requirement. De Novo Subjects will discontinue all current analgesics including their prior opioid medication.

All subjects will begin dosing with 100-mg NKTR-181 BID with dose escalation in stepwise increments of 100-mg (e.g., from 200-mg BID to 300-mg BID) up to a maximum dose of 600-mg BID. All dose escalations will occur prior to visit 10. The dose of NKTR-181 will not exceed 600 mg BID in this study. Subjects will be instructed to take study drug BID, preferably at 8 AM and 8 PM. Subjects will also receive training on the recognition and management of constipation and other opioid related side effects. Side effects should be managed according to standard of care practices.

If a subject cannot tolerate 100-mg NKTR-181 BID, the subject will be discontinued from the study; these subjects will be required to complete the Early Termination (ET) visit (Visit 21/ET) and safety follow-up requirements. Refer to the Schedule of Assessments (Section 1.2) for complete information regarding all assessments to be completed at the ET Visit and safety follow-up requirements.

Within 4-10 days after receiving the first dose of NKTR-181, subjects will return to the clinic at which time the Investigator will assess for tolerability and effectiveness. **Tolerability** and **effectiveness** will be assessed based on Investigator (or qualified sub-Investigator) clinical judgment. The Investigator (or qualified sub-Investigator) will determine whether the subject should remain at the current dose or titrate to the next dose level.

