Subjects will return to the clinic for assessments of tolerability and effectiveness every 4 to 10 days for up to 6 more times over a 5-week period until a stable dose is achieved. A **stable** dose is a dose that is effective and tolerated on two sequential visits (i.e., after at least 8 days of continuous treatment). Subjects who continue to tolerate study drug but do not have adequate relief of pain, based on the Investigator's clinical judgment, will continue dose escalations of 100-mg BID increments until the maximum dose of 600-mg NKTR-181 BID is reached.

Subjects who do not achieve adequate pain control at 600-mg NKTR-181 BID will be classified as non-responders and will be discontinued from further participation in the study.

Non-responders will be required to complete the ET Visit (Visit 21/ET) and safety follow-up requirements.

Subjects will begin a monthly clinic visit schedule after a tolerable, effective and stable dose is achieved. **Doses of NKTR-181 may be adjusted upwards (up to a maximum dose of 600-mg NKTR-181 BID) or downwards as needed during the Treatment Period, based on the Investigator's (or qualified sub-Investigator's) assessment of effectiveness and tolerability.**

If at any time a subject cannot tolerate study drug between protocol-mandated visits, per Investigator discretion, an unscheduled visit should occur. For subjects with tolerability issues, the dose of NKTR-181 may be adjusted downwards, as necessary, based on the Investigator's clinical judgment in a stepwise 100-mg changes (e.g., 300-mg BID may be lowered to 200-mg BID). Dose adjustments may occur at unscheduled visits, however, an unscheduled visit will not replace a regularly scheduled visit, and the subject should be seen at all regularly scheduled visits.

Throughout the Treatment Period, subjects who experience breakthrough pain will be allowed rescue medication, as outlined in Section 6.4. Note: If subject is off of study drug for 3 days or more, sponsor **must** be consulted prior to restarting study drug.

Subjects will report their pain experience at each visit using the mBPI-SF. At quarterly intervals, subjects will be assessed for vital signs, 12-lead electrocardiogram (ECG), and clinical laboratory testing.

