Following 51 weeks of NKTR-181 treatment, subjects will begin a 1-week taper from study drug. The NKTR-181 dose will be decreased over the 1-week period until all subjects are receiving 100-mg BID for at least 2 days. Subjects will return to the site for their End of Treatment visit (Visit 22/EOT). Following completion of Visit 22/EOT **or** completion of an ET Visit at any time after receiving study drug, subjects will proceed to the Safety Follow-Up Period.

The COWS and SOWS will be administered according to the Schedule of Assessments (Section 1.2) to monitor for opioid withdrawal. Subjects experiencing opioid withdrawal will be treated appropriately according to the Investigator's clinical practice.

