7.2 Study Day

- The day of the titration start (Visit 3 date) will be called Titration Day 1. Visit 10 is the end of titration, the dose at visit 10 is defined as stable dose. The day of the stable dose (Visit 10 date) will be called Day I. Study day will be calculated from the Day 1.
- Baseline is defined as the last non-missing observation prior to or on Titration Day 1. Change from baseline variables will be calculated as the post-baseline value minus baseline value.

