7.4 Definition of Visit Window

Deviations are to be expected between subjects in the actual number of study days from Day 1 to when planned visits are carried out. To handle this for tables, figures, listings, and analyses where data are to be grouped by visit, visit numbers will be defined according to [Table 1](#).

The following windows will apply only for summaries for value and change value by visit and summaries for abnormalities. If multiple assessments were performed within the visit window, the following will be applied:

- If there are multiple records in the same visit window, the measurement closest to the scheduled visit day will be used.
- If two visits are equidistant from the scheduled day, the later will be assigned to the visit.
- In the summaries for abnormalities, the worst case will be summarized for that visit regardless of how close to the scheduled visit it is.

Table 1: Windowed Visits for Summary

Visit	Scheduled Study Day	Windowed Visits for Labs	Windowed Visits for Vital Signs	Windowed Visits for ECG	Windowed Visits for CSSRS	Windowed Visits for mBPI	Windowed Visits for COWS
Baseline	First dose	<=first dose date	<=first dose date	<=first dose date	<=first dose date	<=first dose date	<=first dose date
The Titration visits		go with the actual visit	go with the actual visit	NA	NA	go with the actual visit	NA
Visit 10 - Stable Dose	1	Day 1	Day 1	Day 1	Day 1	Day 1	NA
Visit 11	30	Day2 to 45	NA	NA	NA	Day2 to 45	NA
Visit 12	60	Day46 to 75	NA	NA	NA	Day46to 75	NA
Visit 13	90	Day76 to 105	Day2 to 105	Day2 to 105	Day2 to 105	Day76 to 105	NA
Visit 14	120	NA	NA	NA	NA	Day106 to 135	NA
Visit 15	150	NA	NA	NA	NA	Day136 to 165	NA
Visit 16	180	NA	NA	NA	NA	Day165 to 195	NA
Visit 17	210	Day106 to 225	Day106 to 225	Day106 to 225	Day106 to 225	Day196 to 225	NA
Visit 18	240	NA	NA	NA	NA	Day226 to 255	NA
Visit 19	270	NA	NA	NA	NA	Day256 to 285	NA
Visit 20	300	Day226 to one day before visit 21	Day226 to one day before visit 21	Day226 to one day before visit 21	Day226 to one day before visit 21	Day286 to one day before visit 21	NA
Visit 21	357 from Titration Day 1	go with the actual visit	NA	NA	go with the actual visit	go with the actual visit	go with the actual visit
Visit 22	364 from Titration Day 1	go with the actual visit	go with the actual visit	go with the actual visit	go with the actual visit	go with the actual visit	go with the actual visit

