8.6.1 Responder Rates Based on mBPI Pain Intensity

Pain intensity score reduction based on the mBPI Pain Intensity subscale for each visit will be used to classify responder where:

Pain intensity score reduction = (mBPI Pain Intensity change from visit 3/visit 3 mBPI Pain Intensity)*100.

Three responder rates will be calculated at each time point, where responders are defined as subjects with:

- Pain intensity score reduced by 30% from visit 3 mBPI Pain Intensity,
- Pain intensity score reduced by 50% from visit 3 mBPI Pain Intensity,

- Pain intensity score reduced according to multiple cut-offs of 10% increments from the visit 3 mBPI Pain Intensity.

Responder rate = (no. of responders / total no. of subjects)*100, where total no. of subjects is the number of all the subjects in the analysis set. Subjects, who discontinue prior to the time point or have a missing pain score at that time point, will be counted as non-responders.

The number and percentage of responders in each dose level for pain intensity score reduction according to multiple cut-offs of 10% increments from baseline will be presented.

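### SAP Table 1 opens the Visit 20 pain window on a clock started at Visit 10 and closes it on a clock started at first dose, so a late Visit 10 can shorten or remove the window for subjects still on treatment

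*SAP*

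**What the plan says.** SAP 7.2 sets the study-day origin: "The day of the stable dose (Visit 10 date) will be called Day I. Study day will be calculated from the Day 1". The same section calls Visit 10 the end of titration and counts Titration Day 1 from Visit 3. In SAP 7.4, Table 1 schedules Visits 11 to 20 at Days 30 to 300 on the Visit 10 clock. It then puts Visit 21 at "357 from Titration Day 1" and Visit 22 at Day 364 on that same first-dose clock. The Visit 20 mBPI window is "Day286 to one day before visit 21", so its two ends use different clocks.

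The first-dose anchor for Visit 21 agrees with protocol 6.2: "Following 51 weeks of NKTR-181 treatment, subjects will begin a 1-week taper from study drug". The Schedule (protocol 1.2) gives Visit 21 as Day 357 with a +3 allowance.

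The documents disagree on when Visit 10 falls. Protocol 6.2 has a first return visit "Within 4-10 days after receiving the first dose of NKTR-181" and then visits "every 4 to 10 days for up to 6 more times over a 5-week period until a stable dose is achieved". The Schedule spaces Visits 4 to 9 "Every 4-10 Days after previous visit" but puts Visit 10 in the same column as Visits 13, 17 and 20, every 30 days with a 3-day early allowance.

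SAP 8.6.1 keeps every subject of the analysis set in the responder denominator. Subjects who have discontinued, or who "have a missing pain score at that time point, will be counted as non-responders".

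**The concern.** A subject with a late Visit 10 reaches the fixed end of treatment before ten monthly visits have elapsed. Visit 20 then has a shortened window or none, although the subject is on drug and attending. The Schedule lists no mBPI-SF at Visit 21, and the Visit 22 score follows the 1-week taper, so Visit 20 is the last scheduled pain score before the taper. At stake are the Visit 20 pain means and, depending on how 8.6.1 is read, the Visit 20 responder rate, which could record non-response for a visit that was never due.

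Separately, Table 1 gives Day 165 to both Visit 15 (Days 136 to 165) and Visit 16 (Days 165 to 195) for mBPI.

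**Working it through.** **Reproducing the plan's figures.** Each lower bound in Table 1 is the midpoint of adjacent scheduled days plus 1.
- Visit 20: (270 + 300)/2 + 1 = 286, as printed.
- Visit 16: (150 + 180)/2 + 1 = 166. Table 1 prints 165, hence the overlap.
- Visit 21: 51 weeks × 7 = 357, as printed.

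**One clock.** Let T be the titration day of Visit 10. Titration day d is study Day d − T + 1.
- Visit 21 is study Day 357 − T + 1 = 358 − T.
- The Visit 20 mBPI window is Day 286 to Day 357 − T (Day 360 − T if Visit 21 uses its +3 days).

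**Thresholds.**
- Scheduled Day 300 is excluded when 357 − T < 300, so T ≥ 58 (T ≥ 61 with +3).
- With visits exactly 30 days apart, Visit 20 falls on Day 1 + 10 × 30 = 301, and the threshold is T ≥ 57 (T ≥ 60 with +3).
- The window has no days when 357 − T < 286, so T ≥ 72 (T ≥ 75 with +3).
- The Visit 20 windows for labs, vital signs, ECG and C-SSRS open at Day 226. They lose all days only when 357 − T < 226, so T ≥ 132.

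**Values of T under each reading** (Visit 21 on Day 357):

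| Timing of Visit 10 | T | Visit 20 mBPI window | Holds Day 300? |
|---|---|---|---|
| Closes titration, 5 weeks in all (1 + 35) | 36 | 286–321 | Yes |
| Closes titration, 10 + 35 days (1 + 45) | 46 | 286–311 | Yes |
| Six 4-day steps, then 27–30 days | 52–55 | 286–305 to 286–302 | Yes |
| 5 weeks in all, then 27–30 days | 63–66 | 286–294 to 286–291 | No |
| Six 7-day steps, then 27 days | 70 | 286–287 | No |
| Six 7-day steps, then 30 days | 73 | none | No |
| 10 + 35 days, then 27–30 days | 73–76 | none | No |
| Six 10-day steps, then 27–30 days | 88–91 | none | No |

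With Visit 21 at +3 days, T = 73 leaves Days 286–287. The last row meets the Schedule's spacing but puts Visit 9 on Day 61, beyond the 10 + 35 days of protocol 6.2.

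**Nominal visits, without windows.** Visit 20 at study Day 300 is titration day T + 299. For T = 46 this is Day 345, before Visit 21. For T = 73 it is Day 372, after Visit 21. The visit can therefore be absent even if Table 1 is not used for responder rates.

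**Shorter cadence.** Once T ≥ 72 and Visit 21 is on Day 357, any score before Visit 21 falls on Day 285 or earlier, in the Visit 19 window or before. More frequent visits do not restore Visit 20.

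**The case against.** Four points count on the other side.

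- **Visit 10 timing.** SAP 7.2 calls Visit 10 the end of titration. Protocol 6.2 gives one return visit plus up to six more, which is seven visits and matches Visits 4 to 10. On that reading T is at most 46 and the windows fit. The contrary evidence is the Schedule column that Visit 10 shares with later monthly visits. This stands as a reason to treat the problem as conditional. It does not remove the conflict between the passages.
- **Scope of Table 1.** SAP 7.4 first applies the table to all analyses grouped by visit, then restricts the windows to value and change summaries and abnormality summaries. Responder rates are in neither class. A reader might infer that an empty window makes a subject a non-responder, but the documents do not establish that. The loss from value and change summaries is expressly covered, and the nominal-visit route to non-response remains open.
- **Consequence.** A reader might also infer that long-term responder rates are biased by construction against slow titrators. The documents do not support this. The effect needs a late Visit 10, concerns Visit 20, and leaves the Visit 22 score unaffected because Table 1 assigns Visit 22 by actual visit. A subject without a score is absent from a visit mean, not failed in it.
- **Choice of origin.** Counting from the stable dose is legitimate. That visit numbers then stand for different times on drug follows from the choice and is not an error.

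**Conclusion.** The two-clock defect in the Visit 20 mBPI window is real, and its effect is conditional. The window misses scheduled Day 300 from T = 58 and has no days from T = 72 (61 and 75 with the +3 allowance). This happens if Visit 10 follows the last flexible visit by 27 to 30 days and titration is not short. It does not happen if Visit 10 closes the 5-week titration.

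Where it happens, subjects on treatment leave the Visit 20 value and change summaries. They may also be scored as non-responders, either because Table 1 is taken to govern 8.6.1 or because Visit 20 is not due before Visit 21.

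The documents give no distribution of Visit 10 dates, so the number affected is unknown. The impact is on descriptive secondary efficacy results, not on the primary safety objective. The double claim on Day 165 holds without conditions.

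**What to change.** 1. Reconcile protocol 6.2, the Schedule and SAP 7.2 on when Visit 10 takes place.
2. Start the Visit 16 mBPI window at Day 166.
3. State in SAP 7.4 or 8.6.1 whether Table 1 governs the responder rates.
4. For subjects who reach the scheduled Day 357 Visit 21 before their Visit 20 is due, do not count the absent Visit 20 score as non-response. Either report them as not scheduled at Visit 20, or add a sensitivity summary by time since Titration Day 1. Keep early terminators in the denominator as non-responders.

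Two simpler remedies should be avoided. Excluding everyone whose Visit 21 falls on or before study Day 286 would also drop early terminators, because Visit 21 doubles as the early-termination visit, and so would raise the responder rate. Re-anchoring every long-term window on Titration Day 1 would place early windows inside titration.

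The cost is a few lines in SAP Table 1, 7.4 and 8.6.1 and a clarification of Visit 10 timing. No new data are required.

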6.3 Safety Follow-Up Period (Visits 23-24)

To capture evidence of withdrawal following discontinuation of study drug, all subjects (including ET subjects) will record SOWS measurements and be administered COWS assessments as described in the Schedule of Assessments (Section 1.2).

During the Safety Follow-Up Period, clinical laboratory samples will be collected only if a prior laboratory result was considered abnormal and clinically significant.

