10.10 Opioid Withdrawal

10.10.1 Clinical Opiate Withdrawal Scale (COWS)

Opiate withdrawal will be assessed using the COWS (Wesson, 2003). The scale consists of 11 evaluations of physical components of withdrawal and is based on clinician observations and questions.

The COWS will be administered by the Investigator or qualified sub-Investigator at Visit 3 prior to any other study assessments. The COWS must be ≤ 12 in order for the subject to continue participation in the study. Subjects who score greater than 12 will complete their Screening Period, end study participation, and be treated appropriately for withdrawal according to the Investigator’s clinical practice. A COWS assessment will be administered by the Investigator or qualified sub-Investigator at Visits 3, 21, and 22/EOT (or ET Visit), and during the Safety Follow-Up Period at Visits 23 and 24/EOS. Subjects experiencing opioid withdrawal will be treated appropriately according to the Investigator’s clinical practice.

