BID	twice daily
BMI	body mass index
BP	blood pressure
mBPI-SF	Modified Brief Pain Inventory-Short Form
CI	confidence interval
CLBP	chronic low back pain
COWS	Clinical Opiate Withdrawal Scale
CRO	clinical research organization
C-SSRS	Columbia-Suicide Severity Rating Scale
CYP3A	cytochrome P 450 enzyme isoform 3A
ECG	electrocardiogram
eCRF	electronic case report form
eC-SSRS	electronic Columbia-Suicide Severity Rating Scale
ET	early termination
GCP	Good Clinical Practice
GGT	gamma-glutamyl transferase
GSP	Good Statistical Practice
ICF	informed consent form
ICH	International Conference on Harmonisation
IXRS	Interactive Voice and Web Response System
MADDERS™	Misuse, Abuse, and Divergent Drug Event Reporting System
MedDRA	Medical Dictionary for Regulatory Activities

Abbreviation or Term	Definition
MMRM	mixed model repeated measures
NSAID	non-steroidal anti-inflammatory drug
NRS	Numeric Rating Scale
PHQ-8	Personal Health Questionnaire Depression Scale
PK	pharmacokinetic
QTcF	corrected QT interval, Fridericia's correction
RR	respiratory rate
SAP	statistical analysis plan
SOC	system organ class
SOWS	Subjective Opiate Withdrawal Scale
TBL	total bilirubin
TEAE	treatment-emergent adverse event
ULN	upper limit of normal
US	United States
WHO	World Health Organization

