3-day Safety Follow-up	3 days after ET visit	3 to 6 days after ET visit	3 to 6 days after ET visit	NA	NA	NA	3 to 6 days after ET visit
14-day Safety Follow-up	14 days after ET visit	>=7 days after ET visit	NA	NA	NA	NA	>=7 days after ET visit

Abbreviations: C-SSRS, Columbia-Suicide Severity Rating Scale; NA, not applicable.

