3.2 Pharmacokinetic Assessment

This study will investigate the PK of NKTR-181 in patients with chronic low back pain or chronic non-cancer pain. Sparse blood samples for PK analysis will be collected from all subjects at follows: Visits 3, 4, 5, 6, 7, 8, 9, 10, 11, 12, 13, 17, 20, 21, 22, Unscheduled visits, end of treatment, and Early Termination visits.

In addition, a subset of approximately 100 subjects will be participating in the PK sub-study. The PK sub-study commences after a stable dose has been identified. This may occur as early as the second visit following the start of the Treatment phase. The PK collection visit will be scheduled to start in the morning, prior to the subject taking their morning dose of NKTR-181. Subjects should be reminded in advance of the visit to hold their morning dose of study drug and to bring their study drug supply to the clinic with them. Subjects will take their morning dose of NKTR-181 in the clinic after a predose PK sample is drawn. PK samples will be obtained 0.5, 1, 2, 3, 4, 5, 6, 8, and 12 hours postdoc.

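### SAP Table 1 times both safety follow-up rows only from the ET (early termination) visit, so completers' Visit 23 and 24 COWS enter neither row

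*SAP*

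**What the plan says.** SAP 7.4 uses Table 1 to assign records to visits for by-visit value and change summaries and for abnormality summaries. The two follow-up rows have a single anchor. The 3-day row takes labs, vital signs and COWS dated "3 to 6 days after ET visit". The 14-day row takes labs and COWS dated ">=7 days after ET visit". Neither row has the rule given to Visits 21 and 22, where the record simply follows the visit at which it was taken.

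The SAP abbreviation list expands ET as "early termination". The protocol schedule keeps two terms apart: "EOT, end of treatment; ET, early termination". Its footnote 2 gives the ET assessments to a dosed subject who "discontinues from the study before completing all of the scheduled assessments, then assessments for Visit 21/ET and all safety follow-up procedures should be completed". Protocol 6.2 describes two routes into follow-up: Visit 22/EOT, or an ET visit.

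Follow-up COWS is meant for everyone. Protocol 6.3 says that "all subjects (including ET subjects) will record SOWS measurements and be administered COWS assessments as described in the Schedule of Assessments", and Protocol 10.10.1 places COWS "at Visits 3, 21, and 22/EOT (or ET Visit), and during the Safety Follow-Up Period at Visits 23 and 24/EOS". SAP 5.0 names withdrawal measured by COWS among the key safety endpoints.

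**The concern.** A subject who finishes treatment and taper attends Visit 21 and Visit 22/EOT and never has an early termination visit. For that subject the days since the ET visit are undefined, and Table 1 offers no other route into the follow-up rows.

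These two rows are the only post-dose COWS rows in the table. Filled as written, they would show withdrawal only in subjects who stopped early. Under schedule footnote 20 those subjects are not dispensed taper drug, so they differ from completers in a way that bears directly on withdrawal scores. A reader of the by-visit table could take the result as describing the whole Safety Analysis Set. Nothing in either document declares such a restriction, and SAP 9.0 reports no change of analysis from the protocol.

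**Working it through.** The plan gives no figure of its own to reproduce. The check is day arithmetic on the visit schedule.

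**Inputs.** Visit 21 is day 357 (+3), Visit 22 day 364 (+3), Visit 23 at 72 hours and Visit 24 at 14 (±2) days (Protocol 1.2; SAP Table 1 for the nominal days of Visits 21 and 22). Visits 23 and 24 are counted from Visit 22, because schedule footnote 17 equates the last dose with Visit 22. The allowed dates are therefore V21 = 357 to 360, V22 = 364 to 367, V23 = V22 + 3 and V24 = V22 + 12 to 16, which makes 4 × 4 × 5 = 80 combinations. These are unweighted calendar combinations, not subjects or probabilities.

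**Completers under three readings of the anchor**

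| Reading of ET visit | Visit 23 | Visit 24 | Result |
|---|---|---|---|
| A. Early termination, as defined | undefined | undefined | neither visit enters a row |
| B. The protocol's shared Visit 21/ET column | day 7 to 13 | day 16 to 26 | 3-day row empty; both fall in the 14-day window |
| C. Visit 22/EOT | day 3 | day 12 to 16 | both in the right row, 80 of 80 |

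**Detail on B.** The gap from Visit 21 to Visit 22 is 4 to 10 days. Adding 3 gives 7 to 13 for Visit 23; adding 12 to 16 gives 16 to 26 for Visit 24. On the nominal schedule Visit 23 is at day 10 (4 days from day 14) and Visit 24 at day 21 (7 days from day 14). The closest-record rule in SAP 7.4 then reports Visit 23 as the 14-day value. Over the 80 combinations Visit 23 is closer in 61, Visit 24 in 14, and 5 are ties. Ties go to the later record, so Visit 24 is reported in 14 + 5 = 19.

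**Detail on C.** Visit 21 lies 4 to 10 days before the anchor and Visit 22 at day 0, so neither can enter a follow-up row.

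**Early terminators.** The lag from last dose to the ET visit is not given; 0 to 10 days is assumed. With V23 = ET + 3 and V24 = ET + 12 to 16 there are 11 × 5 = 55 combinations.
- ET-visit anchor: both visits in the right row in 55 of 55.
- Last-dose anchor: Visit 23 falls at lag + 3, which is within days 3 to 6 only for lags 0 to 3, so 4 × 5 = 20 of 55. At lags 3 to 6 the ET-visit record itself also falls in the 3-day window.

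**Share of subjects affected under A.** Protocol 11.2 targets at least 100 completers of 52 weeks among about 600 dosed: 100/600 = 16.7%. With 200, 300 or 400 completers (assumptions), the share is 33.3%, 50.0% or 66.7%.

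**The case against.** The strongest reply is that this is a label slip and any programmer would see through it. SAP 4.0 defines follow-up as Visits 23 and 24 for the whole study, timed from the last dose. SAP 8.7.2 calculates COWS totals at all scheduled time points. The protocol often pairs the EOT and ET visits as alternatives, and the visible SAP abbreviation list has no EOT entry. End of treatment is probably what was meant, and that reading works. But it contradicts the SAP's definition of ET, and SAP 8.7.2 says only that totals are calculated, not which row they go in. Table 1 is the operative rule, and it has to be overridden to get the right answer.

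Several smaller points stand:
- The PK analysis plan (3.2) lists "Unscheduled visits, end of treatment, and Early Termination visits", which separates the two terms. But it also names Visit 22, so the list is redundant and supports the point only weakly.
- The reach is limited. Completers' COWS at Visits 21 and 22 keep their own rows, and the categorical COWS summary by dose level is not stated to be windowed. Under reading B, abnormality summaries use the worst value, so there Visit 23 would not displace Visit 24.
- The 80 of 80 result follows directly from fixing Visit 23 at Visit 22 + 3. If the last dose is taken the day before Visit 22 and the 72 hours run from it, Visit 23 is day 2 and misses the 3-to-6-day range. No drug is dispensed at Visit 22 (footnote 21), so this could happen, although footnote 17 points the other way.
- If an early terminator's Visit 24 is timed from the last dose, it stays at 7 or more days after the ET visit in 5 of 5 cases for lags 0 to 5, and in 4 of 5 at lag 6.

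These points limit the size of the problem and the precision of the fix. They do not make Table 1 correct as written.

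**Conclusion.** The concern holds, and the table should be corrected. Under the SAP's own definition of ET, no completer contributes to either follow-up row: at least about 17% of subjects at the planning target, and more if more complete. That target is a minimum, and the total of 600 may change, so the share is a guide rather than a forecast. Reading ET visit as the Visit 21/ET column also misplaces Visit 23. Only an end-of-treatment anchor for completers works.

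The consequence is moderate. It affects by-visit and abnormality summaries for follow-up COWS, the 3-day vital signs row, and follow-up labs, which are drawn only after an earlier clinically significant abnormality. Listings, SOWS (which has no column in Table 1) and withdrawal adverse events are unaffected. The confidence is high on the wording; the effect on the output depends on the programmer following Table 1 literally.

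**What to change.** In both follow-up rows of SAP Table 1, including the scheduled-day column, count days after Visit 22/EOT for subjects who complete treatment and after the ET visit for subjects who terminate early. Keep the present day ranges and the cells marked not applicable. State that records from Visit 21, Visit 22 and the ET visit stay in their own rows, and name the row that holds ET-visit records, since Table 1 has none labelled for that visit. A last-dose anchor for everyone is not a good substitute unless the ET visit follows the last dose closely.

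The cost is one table edit and the matching programming. No new data are needed and no study procedure changes.
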